5.2.1.2.3 Dose Modification Guidelines for Dexamethasone

Low-dose dexamethasone will be given at 40 mg once orally on Days 1, 8, 15, and 22 (i.e., once weekly) of repeated 28-day cycles every 28 days. For subjects aged > 75 years in both arms, a daily dexamethasone dose of 20 mg on days 1, 8, 15, and 22 every 28 days is recommended [39].

The criteria presented in this section for dose modification are meant as general guidelines, and they are based on current US standards of clinical practice. Local standards and

prescribing information may differ and should be followed. Dexamethasone dose modifications for toxicity must be performed as clinically indicated at the discretion of the investigator. Refer to the dexamethasone local prescribing information, [Table 7](#), and [Table 8](#) for dose modification guidelines.

Table 7 Supportive Care Guidelines Specific to Dexamethasone

Body System	Symptom	Recommended Action
Gastrointestinal	Dyspepsia, gastric or duodenal ulcer, gastritis Grade 1–2 (requiring medical management)	Treat with H2 blockers, sucralfate, or omeprazole. If symptoms persist despite above measures, decrease dexamethasone dose by one dose level.
Gastrointestinal	> Grade 3 (requiring hospitalization or surgery)	Hold dexamethasone until symptoms adequately controlled. Restart and decrease one dose level of current dose along with concurrent therapy with H2 blockers, sucralfate, or omeprazole. If symptoms persist despite above measures, discontinue dexamethasone and do not resume.
Gastrointestinal	Acute pancreatitis	Discontinue dexamethasone and do not resume.
Cardiovascular	Edema >Grade 3 (limiting function and unresponsive to therapy or anasarca)	Diuretics as needed, and decrease dexamethasone dose by one dose level; if edema persists despite above measures, decrease dose another dose level. Discontinue dexamethasone and do not resume if symptoms persist despite second reduction.
Neurology	Confusion or Mood alteration > Grade 2 (interfering with function +/- interfering with activities of daily living)	Hold dexamethasone until symptoms resolve. Restart with one dose level reduction. If symptoms persist despite above measures, discontinue dexamethasone do not resume.
Musculoskeletal	Muscle weakness > Grade 2 (symptomatic and interfering with function +/- interfering with activities of daily living)	Decrease dexamethasone dose by one dose level. If weakness persists despite above measures, decrease dose by one dose level. Discontinue dexamethasone and do not resume if symptoms persist.
Metabolic	Hyperglycemia > Grade 3 or higher	Treatment with insulin or oral hypoglycemics as needed. If uncontrolled despite above measures, decrease dose by one dose level until levels are satisfactory.

Table 8 Recommended Dose reduction levels for Dexamethasone

Dose Level	Dexamethasone dose (PO)
0	40 mg
-1	20 mg
-2	12 mg
-3	0 mg

5.2.2 Timing of Dose Administration

Subjects in the **investigational arm** (Arm A) should start treatment with all 3 drugs (pembrolizumab, lenalidomide and low-dose dexamethasone) on cycle 1 day 1 (C1D1). After C1D1, pembrolizumab infusions will continue every 21 days (Q3W). Lenalidomide administrations will continue daily, on days 1-21 and low-dose dexamethasone administrations will continue daily, on days 1, 8, 15, and 22 of repeated 28-day cycles.

In the **control arm (Arm B)**, subjects should start treatment on cycle 1 day 1 (C1D1) with both lenalidomide and low-dose dexamethasone. Lenalidomide administrations will continue daily, on days 1-21 and low-dose dexamethasone administrations will continue daily, on days 1, 8, 15, and 22 of repeated 28-day cycles.

NOTE: For subjects aged > 75 years in both arms, a daily low-dose dexamethasone dose of 20 mg on days 1, 8, 15, and 22 of repeated 28-day cycles is recommended when combined with pembrolizumab and lenalidomide or with lenalidomide alone [39].

All subjects under treatment with lenalidomide must receive appropriate anti-coagulation prophylaxis therapy. The appropriate anti-coagulation prophylaxis treatment should be selected according to institutional practice. Examples of commonly used thrombo-embolic prophylaxis medications include aspirin, low molecular weight heparin, and vitamin K antagonists.

Trial treatment of pembrolizumab may be administered up to 3 days before or after the scheduled Day 1 of each cycle due to administrative reasons. Trial treatment of lenalidomide and low-dose dexamethasone may be administered up to 3 days before or after the scheduled dosing date for administrative reasons per the investigator's judgment. Missed doses should be skipped, not delayed, if not given within the allowed window.

Dosing interruptions are permitted in the case of medical / surgical events or logistical reasons (e.g., elective surgery, unrelated medical events, radiotherapy, patient vacation, and holidays) not related to study therapy. Subjects should be placed back on study therapy within 28 days of the scheduled interruption. The reason for interruption should be documented in the subject's study record. Dosing interruptions should be discussed with the Sponsor.

Delays for 12 weeks between pembrolizumab doses due to toxicity or delays for 28 days between lenalidomide or low-dose dexamethasone doses due to toxicity are also permitted. However, disease response assessments should continue to be performed according to schedule as detailed on the Trial Flow Chart (Section 6.0), independently of doses delays for both treatment groups. Dose delays should be discussed with the Sponsor.

For both groups, if the dose of one drug in the regimen (i.e., pembrolizumab, lenalidomide, or low dose dexamethasone) is delayed or interrupted the treatment with the other drugs may continue as scheduled. Missed doses should be skipped, not delayed, if not given within the allowed window (+/- 3 days). If either pembrolizumab, lenalidomide or low-dose

dexamethasone is discontinued due to unacceptable toxicity, subjects can continue to receive study treatment with the remaining study drugs without discontinuing from study.

Details on the preparation and administration of pembrolizumab are provided in the Pharmacy Manual. For details on the administration of lenalidomide or low-dose dexamethasone, please refer to the local prescribing information.

5.2.2.1 Pembrolizumab

Trial treatment of pembrolizumab should start on cycle 1 day 1 (C1D1) and continue every 21 days (Q3W) after all procedures/assessments have been completed as detailed in the Trial Flow Chart (Section 6.0).

Pembrolizumab 200 mg will be administered as a 30-minute IV infusion every 21 days (Q3W). Sites should make every effort to target infusion timing to be as close to 30 minutes as possible. However, given the variability of infusion pumps from site to site, a window of -5 minutes and +10 minutes is permitted (i.e., infusion time is 30 minutes: -5 min/+10 min).

The Pharmacy Manual contains specific instructions for the preparation of the pembrolizumab infusion fluid and administration of infusion solution.

5.2.2.2 Lenalidomide

Trial treatment of lenalidomide should start on cycle 1 day 1 (C1D1). Lenalidomide PO 25 mg will be given daily on days 1-21 of repeated 28-day cycles. Subjects should be instructed that if a dose of lenalidomide has been missed and it has been less than 12 hours since the subject's regular dosing time, the subject should take lenalidomide as soon as the subject remembers. If it has been more than 12 hours, the dose must be skipped. Subjects should not take 2 doses at the same time. All subjects under treatment with lenalidomide must receive appropriate anti-coagulation prophylaxis therapy which should be selected according to institutional practice. Examples of commonly used thrombo-embolic prophylaxis medications include aspirin, low molecular weight heparin, and vitamin K antagonists. For details on the administration of lenalidomide, please refer to the local prescribing information.

5.2.2.3 Dexamethasone

Trial treatment of low-dose dexamethasone should start on cycle 1 day 1 (C1D1). Low-dose dexamethasone PO 40 mg will be given daily, on days 1, 8, 15, and 22 of repeated 28-day cycles. Missed doses should be skipped, not delayed, if not given within the allowed window (+/- 3 days). For details on the administration of low-dose dexamethasone, please refer to the local prescribing information.

NOTE: For subjects aged > 75 years in both arms, a daily low-dose dexamethasone dose of 20 mg on days 1, 8, 15, and 22 of repeated 28-day cycles is recommended when combined with pembrolizumab and lenalidomide or with lenalidomide alone [39].

5.2.3 Extent of Trial Treatment

All subjects who experience a complete response, very good partial response, a partial response, minor response or have stable disease may remain on treatment until documented confirmed disease progression, unacceptable AEs, intercurrent illness that prevents further administration of treatment, subject withdraws consent, pregnancy of the subject, noncompliance with trial treatment or procedure requirements or administrative reasons.

On 03-JUL-2017, the US FDA placed KN183, KN185 and cohort 1 of KN023 on clinical hold based on safety data from KN183 and KN185 presented to the DMC. The FDA determined that the risks of pembrolizumab plus pomalidomide or lenalidomide outweighed any potential benefit for patients with multiple myeloma. Based on this decision, the treatment phase of KN183 and KN185 is closed effective immediately. All subjects must stop study treatment, complete the Discontinuation Visit and move into the long-term safety and survival follow-up per protocol.

5.2.4 Trial Blinding/Masking

This is an open-label trial; therefore, the Sponsor, investigator and subject will know the treatment administered.

5.3 Randomization or Treatment Allocation

Treatment allocation/randomization will occur centrally using an interactive voice response system / integrated web response system (IVRS/IWRS). There are 2 treatment arms. Subjects will be assigned randomly in a 1:1 ratio to treatment with pembrolizumab in combination with lenalidomide and low-dose dexamethasone (investigational arm, Arm A) or lenalidomide and low-dose dexamethasone (control arm, Arm B), respectively.

5.4 Stratification

Treatment allocation/randomization will be stratified according to the following factors:

1. Age (<75 vs. ≥75 years old)
2. International Staging System stage (ISS I or II vs. ISS III)

5.5 Concomitant Medications/Vaccinations (Allowed & Prohibited)

Medications or vaccinations specifically prohibited in the exclusion criteria are not allowed during the ongoing trial. If there is a clinical indication for any medication or vaccination specifically prohibited during the trial, discontinuation from trial therapy or vaccination may be required. The investigator should discuss any questions regarding this with the Sponsor Clinical Director. The final decision on any supportive therapy or vaccination rests with the investigator and/or the subject's primary physician. However, the decision to continue the subject on trial therapy or vaccination schedule requires the mutual agreement of the investigator, the Sponsor and the subject.

5.5.1 Acceptable Concomitant Medications

All treatments that the investigator considers necessary for a subject's welfare may be administered at the discretion of the investigator in keeping with the community standards of medical care. All concomitant medication will be recorded on the case report form (CRF) including all prescription, over-the-counter (OTC), herbal supplements, and IV medications and fluids. If changes occur during the trial period, documentation of drug dosage, frequency, route, and date may also be included on the CRF. Subject may remain on anti-coagulation therapy as long as the PT or PTT is within therapeutic range of the intended use of anticoagulants

All concomitant medications received within 28 days before the first dose of trial treatment and 30 days after the last dose of trial treatment should be recorded. Concomitant medications administered after 30 days after the last dose of trial treatment should be recorded for SAEs and ECIs as defined in Section 7.2.

5.5.2 Prohibited Concomitant Medications

Subjects are prohibited from receiving the following therapies during the Screening and Treatment Phase (including retreatment for post-complete response relapse) of this trial:

- Antineoplastic systemic chemotherapy or biological therapy
- Immunotherapy not specified in this protocol
- Chemotherapy not specified in this protocol
- Investigational agents other than pembrolizumab
- Radiation therapy

Note: Palliative localized radiation therapy to a site of pre-existing disease is permitted while on study.

Note: For subjects in the investigational arm (Arm A) concomitant radiation may be permitted after consultation with the Sponsor for subjects with confirmed disease progression based on the development of new bone lesions or soft tissue plasmacytomas or a definite increase in the size of existing bone lesions or soft tissue plasmacytomas who in the opinion of the investigator may have a tumor flare reaction but otherwise is deriving clinical benefit from study treatment.

- Oral contraceptive
- Live vaccines within 30 days prior to the first dose of trial treatment and while participating in the trial. Examples of live vaccines include, but are not limited to, the following: measles, mumps, rubella, chickenpox, yellow fever, rabies, Bacillus Calmette-Guerin (BCG), and oral typhoid vaccine. Seasonal influenza vaccines for injection are generally killed virus vaccines and are allowed; however intranasal influenza vaccines (e.g., FluMist®) are live attenuated vaccines, and are not allowed.
- Glucocorticoids for any purpose other than to modulate symptoms from an adverse event, serious adverse event, or for use as a pre-medication when required.

Replacement doses of steroids (for example, prednisone 5-7.5 mg daily) are permitted while on study.

Subjects who, in the assessment by the investigator and after consultation with the Sponsor, require the use of any of the aforementioned treatments for clinical management should be removed from the trial. Subjects may receive other medications that the investigator deems to be medically necessary.

The Exclusion Criteria describe other medications which are prohibited in this trial.

There are no prohibited therapies during the Post-Treatment Follow-up Phase. Subjects must be discontinued from the active follow-up phase if they begin a non-trial treatment for their underlying disease.

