- Counseling about pregnancy precautions and the potential risks of fetal exposure must be conducted at a minimum of every 28 days.
- If pregnancy or a positive pregnancy test does occur in the partner of a male subject while taking lenalidomide, the investigator must be notified immediately.

5.7.4.4.2.3 Additional Precautions

- Subjects should be instructed to never give lenalidomide to another person.
- Subjects should be instructed to return any unused capsules to the study doctor.

- Subjects should not donate blood while receiving lenalidomide, during dose interruptions and for at least 28 days after the last dose of lenalidomide.
- No more than a 28-day lenalidomide supply may be dispensed with each cycle of lenalidomide.
- If a subject inadvertently becomes pregnant while on treatment with pembrolizumab, lenalidomide and low dose dexamethasone, the subject will immediately be removed from the study and the Sponsor should be notified by the site without delay within 24 hours.
- Study investigators from United States sites should report any suspected fetal exposure to lenalidomide to Celgene Corporation (at ^{PPD} [REDACTED]) and to FDA via the MedWatch Program (at ^{PPD} [REDACTED]).

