5.8 Subject Withdrawal/Discontinuation Criteria

Subjects may withdraw consent at any time for any reason or be dropped from the trial at the discretion of the investigator should any untoward effect occur. In addition, a subject may be withdrawn by the investigator or the Sponsor if enrollment into the trial is inappropriate, the trial plan is violated, or for administrative and/or other safety reasons. Specific details regarding discontinuation or withdrawal procedures; including specific details regarding withdrawal from Future Biomedical Research, are provided in Section 7.1.4 – Other Procedures.

A subject must be discontinued from the trial for any of the following reasons:

- The subject or legal representative (such as a parent or legal guardian) withdraws consent.

A subject must be discontinued from treatment (but may continue to be monitored in the trial) for any of the following reasons:

- The subject or legal representative (such as a parent or legal guardian) withdraws consent for treatment but agrees to continue to participate in the regularly scheduled study activities.
- Documented disease progression as assessed by the investigator. (i.e., 2 consecutive assessments are needed for disease progression. Clinical deterioration will not be considered progression). Note: Subjects with documented disease progression may continue to receive trial treatment, at the discretion of the study investigator prior consultation with the Sponsor, if they meet the criteria outlined in Section 7.1.2.8.6.
- Unacceptable adverse experiences as described in Sections 5.2.1.2 and 5.6.1.
- Intercurrent illness that prevents further administration of treatment.

- The subject has a confirmed positive serum pregnancy test.
- Subjects who receive any non-protocol specified anti-myeloma therapy prior to documented progression will be discontinued from all study treatment (including lenalidomide and low dose dexamethasone); however, tumor assessments must continue at 4 week intervals until documented progression.
- Noncompliance with trial treatment or procedure requirements.
 - Subjects experiencing a > 12 weeks delay between pembrolizumab doses in the investigational arm (Arm A) or > 28 day delay for both lenalidomide and low dose dexamethasone in the control arm (Arm B) due to an adverse event(s) related to study treatment must be discontinued from treatment.

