7.1.4 Other Procedures

7.1.4.1 Withdrawal/Discontinuation

Subjects who discontinue/withdraw from treatment prior to completion of the treatment regimen should be encouraged to continue to be followed for all remaining study visits.

When a subject discontinues/withdraws from participation in the trial, all applicable activities scheduled for the final trial visit should be performed at the time of discontinuation. Any adverse events which are present at the time of discontinuation/withdrawal should be followed in accordance with the safety requirements outlined in Section 7.2 - Assessing and Recording Adverse Events.

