8.9 Sample Size and Power Calculations

The study will randomize approximately 640 subjects in a 1:1 ratio among the two treatment arms: pembrolizumab in combination with SOC (combination therapy), and SOC (control).

The interim PFS analysis will be performed after approximately 115 PFS events accrue, this will occur ~20 months after the first subject is enrolled.

If the PFS null hypothesis is neither accepted nor rejected at the time of the interim analysis, then a final PFS analysis will be conducted after approximately 227 PFS events have been observed in the trial.

An OS analysis will be performed after approximately 195 deaths have occurred.

The primary endpoint of the study is PFS. The study has ~90% power to detect a hazard ratio of 0.65 (pembrolizumab in combination with SOC vs. SOC) at alpha = 2.5% (one-sided). The sample size calculation is based on the following assumptions: 1) progression-free survival follows an exponential distribution with a median of 25.5 months in the control arm, 2) an enrollment period of 18 months and at least 12 months follow-up, and 3) a cumulative dropout rate of 2% at the end of the first year and 5% at 4 years.

The secondary endpoint of the study is OS. Assuming that the PFS null hypothesis is rejected, the study has ~70% power to detect a hazard ratio of 0.70 (pembrolizumab in combination with SOC vs. SOC) at $\alpha = 2.5\%$ (one-sided). These calculations are based on the following assumptions: 1) OS follows an exponential distribution with 70% overall survival at 36 months in the control arm (Arm B), 2) an enrollment period of 18 months and at least 38 months follow-up, and 3) the same dropout rate as above.

The assumed median PFS and OS in the control arm (Arm B) are observed from standard of care in patients with previously untreated multiple myeloma who are ineligible for SCT [39].

The sample size and power calculations were performed using EAST 6 software.

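### Sections 5.5.2, 5.8 and 5.7.4.4.2.3 remove some subjects from the trial, while other sections stop treatment only; the conflict puts OS and PFS follow-up of those subjects at risk

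*Combined protocol and SAP*

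**What the plan says.** Three rules take a subject out of the trial:

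- **5.5.2**, during Screening and Treatment: subjects who, on the investigator's assessment and after Sponsor consultation, "require the use of any of the aforementioned treatments for clinical management should be removed from the trial". The list covers unplanned systemic anticancer therapy, non-exempt radiation and glucocorticoids, live vaccines and oral contraceptives.
- **5.8, opening paragraph**: a subject may "be dropped from the trial at the discretion of the investigator should any untoward effect occur".
- **5.7.4.4.2.3**: if a subject becomes pregnant on the three-drug regimen, "the subject will immediately be removed from the study".

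Other text points the other way:

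- **5.5**, on the same situation as 5.5.2, says only that "discontinuation from trial therapy or vaccination may be required".
- **5.8** gives withdrawal of consent as its one mandatory reason for leaving the trial. A confirmed positive pregnancy test, unacceptable adverse experiences and non-protocol anti-myeloma therapy before progression all sit in its treatment-only list. For the last of these, "tumor assessments must continue at 4 week intervals until documented progression".
- **1.0 and 2.1** say that all subjects are followed for OS until death, withdrawal of consent or study end.
- **7.1.4.1** says that subjects who stop treatment early "should be encouraged to continue to be followed for all remaining study visits". For a subject who leaves the trial, it asks only for the final-visit activities.

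**The concern.** The ITT population in 8.5.1 keeps every randomized subject, but a subject whose follow-up ends contributes only censored time. Under Tables 15 and 16, PFS is censored at the last disease assessment and OS at the last date known alive. Both analyses then assume that the subject's later risk matches that of subjects still followed.

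That assumption is doubtful when the reason for leaving is an untoward effect, judged by someone who knows the treatment arm. If such removals were more frequent in one arm and were followed by higher mortality, the OS comparison would be biased in favour of that arm. OS carries the most weight here, because the trial was put on clinical hold on safety data.

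**Working it through.** **Does removal end follow-up?** Section 7.1.4.1 treats stopping treatment and leaving the trial as different things, and only the first carries encouragement to continue visits. Section 5.10 lists discontinuing from the trial beside loss to follow-up. Under 7.1.5.5.1, routine survival follow-up starts at confirmed progression or new anti-myeloma therapy. The cases compare as follows:

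| Reason | Removal rule | Other rule | Routine entry to survival follow-up? |
|---|---|---|---|
| Non-protocol anti-myeloma therapy | 5.5.2 | 5.8: stop treatment, keep assessing | Yes (5.8, 7.1.1.5.4, 7.1.5.5.1) |
| Untoward effect | 5.8 opening | 5.8 list: stop treatment for unacceptable adverse experiences | No trigger met |
| Non-exempt steroid or live vaccine | 5.5.2 | 5.5: stopping therapy may be required | No trigger met |
| Pregnancy | 5.7.4.4.2.3 | 5.8 list: stop treatment | No trigger met |

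In the last three rows, follow-up depends on which passage the site applies. The general statement in 1.0 and 2.1 would keep these subjects; the removal wording would not.

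**The plan's own figures.** Section 8.9 and the SAP summary in 8.1 use one-sided 2.5%, 1:1 allocation and 640 subjects.

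- PFS events by Schoenfeld: 4(1.960 + 1.282)² / (ln 0.65)² = 226.5, so 227. Power = Φ(½√227 × 0.4308 − 1.960) = Φ(1.285) = 90.1%.
- OS power with 195 deaths at HR 0.70: Φ(½√195 × 0.3567 − 1.960) = Φ(0.530) = 70.2%.

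Both match the plan, which also assumes "a cumulative dropout rate of 2% at the end of the first year and 5% at 4 years".

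**Extra removal, equal in both arms and unrelated to outcome.** Inputs are exponential survival (control PFS median 25.5 months; control OS 70% at 36 months), 18-month uniform accrual and the plan's dropout. The removal rate is assumed.

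| Extra removal per year | PFS events, month 30 | Power | Deaths, month 56 | Power |
|---|---|---|---|---|
| 0% | 232 | 90.7% | 202 | 71.8% |
| 2% | 228 | 90.2% | 195 | 70.2% |
| 5% | 223 | 89.5% | 184 | 67.8% |
| 10% | 213 | 88.2% | 168 | 63.7% |

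Both analyses are event-driven, so in practice this costs mainly time.

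**Removal related to outcome.** Simulation of the 8.9 OS model (monthly control hazard −ln 0.70/36 = 0.0099), with cutoff at month 56, removal uniform over months 0 to 18 and the death hazard multiplied after removal. The first HR comes from complete follow-up, the second from censoring at removal. There is no treatment effect apart from that of removal.

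| Removed, A / B | Hazard after removal | Deaths lost | HR, full → censored |
|---|---|---|---|
| 5% / 2% | 2–3× | – | shift of 0.02–0.03 |
| 10% / 5% | 2–3× | 9–12% | 1.03–1.05 → about 1.00 |
| 15% / 5% | 3× | 15% | 1.11 → 1.00 |
| 5% / 5% or 10% / 10% | 3× | – | no change |
| 10% / 5% | unchanged | – | no change |

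The 10% / 5% case averages (10 + 5)/2 = 7.5% removed within 18 months, against a planned 5% dropout over four years.

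**Effect on the test.** If a share m of Arm A deaths alone went unobserved under a true HR of 1, the apparent HR is about 1 − m. The one-sided rejection rate at 195 deaths is Φ(½√195 × [−ln(1 − m)] − 1.960). For m = 2%, 5% and 10% this gives 3.4%, 5.5% and 11.0%, against a nominal 2.5%.

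**The case against.** A reader might infer that vital status and progression **are lost** for these subjects. The documents do not support that. Sections 1.0 and 2.1 promise OS follow-up for all subjects and do not name removal as an ending. New anti-myeloma therapy, the most prognostic item in 5.5.2, leads into survival follow-up under 7.1.1.5.4 and 7.1.5.5.1. Section 7.1.5.6 and footnote p of the flow chart let the Sponsor request survival status, excluding only subjects with a recorded death. All of this stands, and it narrows the gap to the last three rows of the first table.

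A reader might also infer that steroid treatment of pembrolizumab toxicity would remove more Arm A subjects. It would not: 5.5.2 exempts glucocorticoids given for adverse events, as premedication or as replacement, and it permits palliative local radiation. What remains is the discretionary clause opening 5.8.

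For PFS, part of the lost information has another source. Sections 7.1.5.5 and 7.1.2.8.5 stop disease assessment at new anticancer treatment. Table 15 censors before that treatment when no progression or death is recorded, and its Sensitivity Analysis 2 counts treatment discontinuation or new therapy as an event. OS has no comparable analysis for removed subjects.

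Finally, 5.5.2 lapses after treatment ("There are no prohibited therapies during the Post-Treatment Follow-up Phase"). Treatment closed after the clinical hold of 03-JUL-2017, and the remaining participants are in survival follow-up. The eligibility rules also make pregnancy and contraceptive use rare. These points lower the severity and change the remedy, but they do not resolve the contradiction or show how subjects already removed were handled.

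**Conclusion.** The contradiction is certain; its effect on the results is not known. Read literally, the removal rules allow informative censoring of ITT subjects in OS, and to a lesser extent in PFS. The exposed group is subjects dropped for an untoward effect, a non-exempt steroid, a live vaccine or pregnancy.

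The conclusion that an OS harm was masked does not follow. The documents give no removal rate, no arm imbalance and no mortality after removal. Every HR shift shown is illustrative and needs **both** unequal removal by arm **and** a higher hazard after removal; without either one, the shift disappears. Within the assumed range, the OS HR moves by about 0.02 to 0.11. Removal unrelated to outcome, at 5% per year, costs about 1 point of PFS power and 4 points of OS power at the planned calendar times.

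Severity: should-fix.

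**What to change.** 1. Reword 5.5.2, the opening of 5.8 and 5.7.4.4.2.3 so that they bear on study treatment only, and state that only withdrawal of consent for follow-up ends survival follow-up and disease assessment. When treatment should stop is a clinical matter for the sponsor and is not addressed here.
2. Reconcile the continued 4-weekly assessments in 5.8 after non-protocol anti-myeloma therapy with the stop at new anticancer treatment in 7.1.5.5 and 7.1.2.8.5, and with the matching sentence at the end of 5.5.2. Referring removed subjects to 7.1.5.5 alone would not settle this, because that section has its own stop rule.
3. Reconcile the oral contraceptive entry in 5.5.2 with the hormonal methods listed in 5.7.4.3.1.
4. Because treatment is closed, seek vital status for subjects already removed, where consent permits. Report removals by arm and reason in the CSR, and add an OS sensitivity analysis for these subjects. Section 8.0 already allows for analysis changes to be reported in the CSR.

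The cost is minor wording, a few contacts of a kind the protocol already defines and one additional analysis. No further subjects are needed.
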